9.4 STATISTICAL ANALYSES

9.4.1 GENERAL APPROACH

All testing described below assumes a significance threshold of $p = 0.05$. All hypothesis tests that are observed to not be statistically significant will be reported as being inconclusive. Continuous data will be described using means and standard deviations, while categorical data will be described using counts/percentages. All statistical estimates of population parameters will be tabulated along with their corresponding confidence intervals (CIs).

Sensitivity analyses will be used to evaluate the robustness of the main results to reasonable perturbations of the statistical models and assumptions used.

[name] will be responsible for statistical computations for data analyses. During the initial data analysis phase, [name] will be blinded to whether data and results are from sham vs active treatment in compliance with the UNC School of Medicine Conflict of Interest Committee proposed financial conflict of interest management plan.

9.4.2 ANALYSIS OF THE PRIMARY EFFICACY OUTCOME MEASURE(S)

We will perform spectral analysis of resting state EEG from day 1 of stimulation (baseline) to day 5 of stimulation. We will use a general linear mixed-effects model (GLMM) to assess if there is statistically significant interaction between treatment (sham/placebo, theta-tACS and alpha-tACS) and session (baseline/Day 1 of stimulation, day 5 of stimulation, 2-week follow-up, 4-week follow-up). Spectral analysis will be performed with multitapered estimation of the frequency spectrum followed by integration over the classical alpha EEG band (usually 8-12 Hz). In a separate analysis, we will perform spectral analysis of resting state EEG before and after each separate stimulation session. These analyses will be completed on the per-protocol dataset.

In our previous study, which used a 5-day protocol in patients with depression (Alexander et al., 2019), we found that a correlation between the log-transformed baseline alpha power (dB) and the alpha power changes at the end of the intervention (Day 5) in all regions. We chose to use the log-transformed baseline alpha power as a covariate. We will use this same covariate in these analyses as well.

Results from this section will be described in mean decibel (dB) change and presented using spectral images for visualization.

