3 OBJECTIVES AND OUTCOME MEASURES

OBJECTIVES	OUTCOME MEASURES	JUSTIFICATION
Primary		
To investigate the physiological changes in patients with systemic lupus erythematosus over the course of a 5-day, 40-minute stimulation protocol, specifically changes in alpha oscillation power from resting-state EEG recordings from baseline (Day 1) to Day 5 of stimulation.	Resting state EEG recordings taken on Day 1 and Day 5 of stimulation.	The protocol is for a 5-day intervention. The primary objective is focused on looking at the change in brain activity over the course of the intervention. Long-term effects (2-week follow-up and 4-week follow-up) will be assessed as exploratory outcomes.
Secondary		
To elucidate the relationship between changes in EEG and changes in pain and depression symptoms, by comparing the changes in symptoms and the change in alpha oscillation power over the course of the intervention (baseline to day 5 of stimulation). The SF-36 will be evaluated at screening and 4-week follow-up.	Correlations between clinical assessments and alpha oscillation power (as measured by resting state EEG recordings) from Day 1 and Day 5 of stimulation.	The objective is to target engagement (i.e., if the stimulation paradigm changes brain activity); the secondary objective is to determine if this engagement resulted in behavioral changes.
Exploratory		
To investigate the outlasting effects, if any, of tACS on brain activity and clinical assessments.	Resting state EEG recordings taken on 2-week and 4-week follow up visits.	The objective is to explore if any changes in brain activity persist as long-term effects. Long-term effects are detected at the 2-week and 4-week follow ups.
To investigate whether tACS increases cognitive control signals during cognitive tasks that probe sustained attention, selective attention, and working memory.	Correlations between frontal midline alpha and theta activity (as measured from EEG recordings on D1, D5, 2-week, and 4-week follow up visits) and accuracy at cognitive	We hypothesize that tACS will improve cognitive control. In particular, we hypothesize that alpha frequency tACS will improve performance the most for tasks that require attention (sustained attention and selective attention tasks),

Lupus Brain		Version 1.8
Protocol		4 March 2022

OBJECTIVES	OUTCOME MEASURES	JUSTIFICATION

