9 STATISTICAL CONSIDERATIONS

9.1 STATISTICAL HYPOTHESES

Null hypothesis: There is no difference in changes of alpha frequency power between baseline (Day 1) RSEEG and RSEEG at completion of stimulation (Day 5) between treatment regimens.

Alternate hypothesis: There is a difference in changes of alpha frequency power between baseline (Day 1) RSEEG and RSEEG at completion of stimulation (Day 5) between treatment regimens.

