9.2 SAMPLE SIZE RATIONALE

At this point in time, no clinical trial has been completed using tACS to treat SLE. However, the Carolina Center for Neurostimulation has run several trials similar to this, including a clinical trial assessing the use of tACS to treat depression over the course of a 5-day, 40-minute stimulation paradigm (Alexander et al., 2019).

This study is a critically necessary preliminary step in this line of research. The most important aspects of the study are its exploratory analyses, its provision of point- and interval-estimates of parameters of interest, and the logistical feasibility and tolerability information it will provide. The levels of precision of the estimators of interest are important; e.g., based on a previous tACS intervention study (Alexander et al., 2019) with a mean alpha oscillatory difference of ~ 2 and $SD \approx 1.2$ and alpha set at .05, we anticipate $N=20$ per group will provide more than 80% power. The effect size was based off the difference between active tACS and sham stimulation. This study will also provide an initial indication of whether it is plausible that tACS may have beneficial effects for the target lupus population. Based on the anticipated

precision of estimators, power levels of test procedures, availability of research subjects, and stage of this line of research, we believe the study is likely to achieve its specific aims; i.e., there is low risk the study will be uninformative/inconclusive.

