9.4.8 EXPLORATORY ANALYSES

We have previously described two exploratory outcomes:

Lupus Brain		Version 1.8
Protocol		4 March 2022

1. To investigate the outlasting effects, if any, of tACS on brain activity and clinical measures.
2. To investigate whether tACS increases cognitive control signals during cognitive tasks that probe sustained attention, selective attention, and working memory.

For (1), we will follow the same analyses as described in 9.4.2 through the two follow-up visits. For (2), we will calculate correlations between frontal midline alpha and theta activity (as measured from EEG recordings) and accuracy at cognitive tasks (reaction time for attention tasks, accuracy for working memory task). The resulting data may be used as covariates (if deemed appropriate) or may just be used as preliminary data for future studies.

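### The primary test in 9.4.2 spans four sessions (6 df), so it can reject the Day 1 to Day 5 null when the arms do not differ at Day 5

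*Combined protocol and SAP*

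**What the plan says.** The primary null in section 9.1, which compares the three arms, reads "There is no difference in changes of alpha frequency power between baseline (Day 1) RSEEG and RSEEG at completion of stimulation (Day 5". The primary objective in the synopsis, section 3 and section 4.1 covers the same interval. Section 3 adds: "Long-term effects (2-week follow-up and 4-week follow-up) will be assessed as exploratory outcomes".

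Section 9.4.2 opens by referring to Day 1 and Day 5. It then specifies a linear mixed model whose test is a "significant interaction between treatment (sham/placebo, theta-tACS and alpha-tACS) and session (baseline/Day 1 of stimulation, day 5 of stimulation, 2-week follow-up, 4-week follow-up"). It gives no Day 5 contrast, no order of testing and no step to follow a significant interaction.

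Section 9.4.8 covers the exploratory question of lasting effects: "we will follow the same analyses as described in 9.4.2 through the two follow-up visits". Section 9.4.1 sets the threshold at 0.05 and says "All hypothesis tests that are observed to not be statistically significant will be reported as being inconclusive".

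On the baseline covariate, 9.4.2 says "We chose to use the log-transformed baseline alpha power as a covariate. We will use this same covariate in these analyses as well". On reporting it says "Results from this section will be described in mean decibel (dB) change".

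**The concern.** The test and the hypothesis are different objects. The interaction null is that the arms do not differ in change at any of the three later visits. The null in 9.1 concerns Day 5 alone. Rejecting the first does not reject the second. A significant primary p-value could come entirely from the follow-ups and still be read as an effect over the intervention week.

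The text also overlaps with itself. If 9.4.2 already contains all four sessions, the extension in 9.4.8 adds nothing, and one p-value serves as both the primary result and an exploratory one. Because 9.4.1 ties reporting to significance, the plan has to say which p-value decides.

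A separate and lesser point is that 9.4.2 does not say whether the response is alpha power or dB change, or how the baseline covariate enters. Baseline appears both as a session level and as a covariate.

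**Working it through.** **Inputs from the documents.** Three arms, 1:1:1 (4.1); four sessions (9.4.2); significance threshold 0.05 (9.4.1); difference about 2, SD about 1.2, 20 per group, power above 80% (9.2); at least 45 evaluable (9.3), so 15 per arm.

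**Assumptions.** The SD of 1.2 is the SD of change. Data are complete. Compound symmetry applies unless stated otherwise. The documents give no follow-up effect, correlation or covariance structure, so those values are illustrative.

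**1. The plan's own power figure.** Two groups, 20 each: 2 / (1.2 × √(2/20)) = 5.27, and 5.27 − 1.96 = 3.31, so two-sided power is 99.95%. The claim of more than 80% is met. At 15 per arm the non-central t gives 99.3%.

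**2. Degrees of freedom.** Test as written: (3−1)(4−1) = 6. Null as stated: (3−1)(2−1) = 2.

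**3. Rejection when the Day 5 null is true.** One arm differs by d at follow-up only. Within-person residual variance = 1.2²/2 = 0.72. Non-centrality λ = n × (sum of squared interaction effects) / 0.72. That sum is (2/3)d² if both follow-ups differ and 0.5d² if only 4 weeks differs. At 15 per arm the error df are 42 × 3 = 126 and the critical F(6, 126) is 2.17.

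- d = 1, both follow-ups: λ = 15 × 0.667 / 0.72 = 13.9
- d = 1, 4 weeks only: λ = 15 × 0.5 / 0.72 = 10.4

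| n per arm | d | 4 weeks only | Both follow-ups |
|---|---|---|---|
| 15 | 0.5 | 17% | 22% |
| 15 | 1.0 | 64% | 79% |
| 20 | 0.5 | 23% | 30% |
| 20 | 1.0 | 79% | 91% |

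Simulation (20,000 trials per scenario) agreed within about one point. The 2-df test of Day 1 to Day 5 change stayed at 4.6–5.4% throughout. When the arms differ nowhere, the 6-df test rejects in about 5%.

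**4. Standardised version.** The effect is sized for 80% power in a pairwise Day 5 ANCOVA at 15 per arm: d = 0.907, 0.838 and 0.629 SD at correlations 0.5, 0.6 and 0.8. The arm differs at follow-up only.

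| Covariance, 6-df test | 4 weeks only | Both follow-ups |
|---|---|---|
| Compound symmetry, random-intercept F | 73–82% | 86–92% |
| AR(1), unstructured (Wilks) | 53–58% | 56–59% |

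A 2-df Day 5 ANCOVA rejects in about 5% in every row. The two rows use different tests. The unstructured test under compound symmetry gives roughly 67–79% and 82–90%. Under AR(1) with no difference anywhere, the random-intercept F itself rejects in about 6–7%.

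**5. Baseline covariate.** A covariate that is constant within a person shifts all of that person's sessions equally, so it cancels from within-person changes. In mixed models fitted to simulated 3 × 15 × 4 data (correlation 0.6):

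- Adding baseline as a main effect left all six interaction estimates and standard errors unchanged to four decimals.
- With 15% of follow-ups missing, the two Day 5 estimates were still unchanged and the follow-up ones moved by up to 0.04.
- Only a baseline-by-session term changed the Day 5 contrast: −0.296 (SE 0.298) became −0.230 (SE 0.288).

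Entered as a main effect, then, the covariate does not adjust for the correlation between baseline and change that 9.4.2 gives as its reason. If the response is dB change instead, Day 1 is zero for everyone and cannot be a session level.

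**The case against.** The strongest reply is that the harm is assumed. The plan nowhere says a significant interaction will be reported as a Day 5 effect. The first sentence of 9.4.2, the null in 9.1 and the wording of 9.4.8 all suggest that a Day 1 and Day 5 primary analysis was meant. Section 9.4.1 also promises confidence intervals for all estimates, so a Day 5 estimate would probably appear. If Day 5 were claimed only when both the interaction and a 2-df Day 5 test were significant, simulation of the standardised scenarios gives a false Day 5 claim in about 3.5–5.5% of trials.

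That last figure is right, but the two-step rule is not in the plan. The rates in the tables are for rejecting the named primary test, not for false statements about Day 5. They would become the latter only if the interaction p-value is taken as the answer, and nothing in the text prevents that. Intention can be inferred in either direction, since the four-session list is explicit.

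It is also fair that the scenario is a demanding one: no effect straight after stimulation and a clear one weeks later. A smaller follow-up effect gives 17–22% at 15 per arm. And this is a pilot whose main product is estimates (9.2). These points limit the weight of the concern. They do not remove the mismatch, because the protocol states a formal primary null and a threshold.

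The covariate point depends on a parameterisation that the plan does not give, so it stands only as a request for clarification.

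**Conclusion.** The concern holds: as written, the primary test in 9.4.2 does not test the primary null in 9.1. The difference in degrees of freedom, 6 against 2, follows from the text once session is a categorical factor, as the four named levels imply.

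The size depends on assumed follow-up effects and correlations. In the scenarios examined, with the Day 5 null true and 15 per arm, the rejection rate runs from 17% to over 90%, against about 5% for a Day 5 test.

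No loss of power is claimed. At the protocol's difference of 2, the 2-df test of change has 99.7% power at 15 per arm. This should be fixed before unblinding, and confidence in the mismatch is high.

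**What to change.** In 9.4.2:

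- Name as the primary test the three-arm (2-df) difference in log alpha power at Day 5, adjusted for baseline log alpha power. State which recording is used; 8.1.1 assigns the before-stimulation recordings to the Day 1 to Day 5 comparison.
- Use only post-baseline sessions as the response. If the follow-ups stay in the model, include a baseline-by-session term and state the covariance structure.
- Report all pairwise arm differences at Day 5 with confidence intervals, including alpha-tACS against sham. Section 9.2 rests on an active-against-sham contrast: "The effect size was based off the difference between active tACS and sham stimulation". State that the 2-df test decides and that the pairwise intervals describe.
- Leave the 2-week and 4-week contrasts to 9.4.8 as exploratory.

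A constrained longitudinal model that keeps Day 1 as a response is also valid, provided the Day 5 contrast is named as primary.

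The cost is a few sentences, with no new data and no change to 9.1. There is one trade-off. Under compound symmetry, if a true effect is equal at Day 5 and 2 weeks and gone by 4 weeks, the 6-df test has about 4–10 points more power (86–92% against 82%). If the effect is at Day 5 only, or equal at all three visits, the adjusted Day 5 test is equal or better (82% against 73–82%).

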8.1.1 PHYSIOLOGICAL CHANGES

1. Resting state EEG (RSEEG) recordings will be completed at several times during the course of the study. On Day 1 and Day 5 of the intervention week, participants will complete an eyes open RSEEG immediately before and after the 40 minutes of stimulation. This measure is used to determine the immediate after-effects of tACS on brain activity, specifically on alpha oscillation power, as well as provide a before-stimulation RSEEG on these dates to compare the baseline (Day 1) to the final day of stimulation. RSEEG will also be recorded at both follow-up visits, to determine the outlasting effects of stimulation, if any. An eyes closed RSEEG will also be collected on Day 1, Day 5, and at both follow-up visits.
2. Sustained attention task will be performed with EEG recorded. The simple reaction time task requires participants to initiate a trial by pressing a button and then when prompted push a different button. In the five-choice serial reaction time task, the task is identical except that the participant is prompted to push one of five different buttons. This task measures sustained attention during the delay period of the task between task initiation and the probe appearing.
3. Selective attention task will be performed with EEG recorded. In this task, participants are instructed to orient attention to either the left or right visual field, or to both. Then, two low contrast Gabor wavelet stimuli are displayed on the screen in the left and right visual field. Each Gabor wavelet is oriented to the left or right. Finally, participants are probed as to the orientation (left or right) of the Gabor wavelet in one visual field. The attention cue to the left or right visual field is 80% predictive of which stimuli will be texted by the probe. Selective attention is the ability to improve performance with a predictive cue relative to an informative cue or an incongruent cue.

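### As specified, the baseline covariate cancels from the primary treatment-by-session test, so the Day 1 to Day 5 comparison is a plain change-score difference without the adjustment the plan intends

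*Combined protocol and SAP*

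**What the plan says.** The primary analysis is in section 9.4.2: "We will use a general linear mixed-effects model (GLMM) to assess if there is statistically significant interaction between treatment" and a second factor given as "session (baseline/Day 1 of stimulation, day 5 of stimulation, 2-week follow-up, 4-week follow-up". Day 1 is therefore part of the modelled response. The same section reports that the earlier depression trial found "a correlation between the log-transformed baseline alpha power (dB) and the alpha power changes at the end of the intervention (Day 5) in all regions", and on that ground adds an adjustment: "We chose to use the log-transformed baseline alpha power as a covariate. We will use this same covariate in these analyses as well". It also states: "Results from this section will be described in mean decibel (dB) change".

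The null hypothesis in 9.1, quoted up to its last word, reads: "There is no difference in changes of alpha frequency power between baseline (Day 1) RSEEG and RSEEG at completion of stimulation (Day 5) between treatment". Section 8.1.1 indicates that the pre-stimulation recordings serve this comparison ("provide a before-stimulation RSEEG on these dates to compare the baseline (Day 1) to the final day of stimulation"), so the covariate and the Day 1 response are the same measurement, up to scale.

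The plan does not state a covariate-by-session term, a random-effects structure or a covariance structure. Nothing says that Day 1 leaves the response once it becomes the covariate. Section 9.4.1 promises sensitivity analyses in general terms and does not name a baseline-adjusted one.

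**The concern.** The plan identifies a problem (change depends on where a participant starts) and names a remedy (adjust for baseline). It then specifies a model in which the remedy does not act on the primary hypothesis. The covariate has one value per participant. As a main effect it can explain differences between participants in overall level, but not differences in change, and the treatment-by-session interaction concerns change only.

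At stake are the width of the interval for the Day 5 arm difference, the sensitivity of that difference to arms that happen to start at different alpha power, and reproducibility. Two analysts working from 9.4.2 could fit different models and report different primary estimates from the same data.

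**Working it through.** **Inputs.** From 9.2, planning values "with a mean alpha oscillatory difference of ~ 2 and $SD \approx 1.2$ and alpha set at .05", with 20 per group. From 9.3, at least 45 evaluable, which at 1:1:1 is 45/3 = 15 per arm. The Day 1/Day 5 correlation (rho) is not in the documents; 0.3 to 0.9 is assumed. Section 9.2 does not say whether 1.2 is the SD of a change or of a single session, so both readings are shown. Two-sided 5% is assumed.

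**1. The plan's own figure.** Normal-approximation power at 20 per arm: 2/(1.2 × √(2/20)) = 5.27, less 1.96 = 3.31, giving 0.9995. The stated bound of more than 80% is met. At 15 per arm: 2/(1.2 × √(2/15)) = 4.56, less 1.96 = 2.60, giving 0.995.

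**2. Cancellation.** Write y(i,s) = arm-by-session mean + β·b(i) + u(i) + e(i,s), with b(i) the baseline covariate. Then y(i,Day 5) − y(i,Day 1) has no term in b(i). The arm contrast is the difference in mean change with or without the covariate.

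REML check on one simulated data set (3 arms × 15, 4 sessions, random intercept):

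| Model | Day 5 vs Day 1 contrast | SE | Interaction Wald (6 df) |
|---|---|---|---|
| No covariate | 0.13743 | 0.33942 | 9.3854 |
| Covariate, main effect | 0.13743 | 0.33942 | 9.3854 |
| Covariate × session | 0.08641 | 0.32820 | 8.8885 |

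The raw change-score difference is 0.13743 and the ANCOVA estimate is 0.08641. The main-effect covariate only lowered the random-intercept variance (0.826 to 0.100). Cancellation also held with dB change or raw power as the response, and with a known unstructured covariance. In a second data set with 15% of follow-up sessions missing, the contrast was still unchanged (0.45291); the SE moved only from 0.3790 to 0.3774.

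**3. What is lost.** With equal session variances s²: variance of change = 2s²(1−rho); variance after adjustment = s²(1−rho²); ratio = (1+rho)/2. The correlation of the change-score contrast with baseline imbalance is −√((1−rho)/2); after adjustment it is about 0. If 1.2 is the SD of change, the unadjusted 95% half-width is 2.048 × 1.2 × √(2/15) = 0.90 at every rho, and the adjusted one is that times √ratio (ignoring the one degree of freedom spent). If 1.2 is a single-session SD, the SEs are 1.2 × √(2(1−rho)) × √(2/15) and 1.2 × √(1−rho²) × √(2/15). A chance Day 1 imbalance of 0.5 SD (0.5 × 1.2 = 0.6 dB) then shifts the change-score contrast by −(1−rho) × 0.6.

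| rho | Variance ratio | Correlation with imbalance | Adjusted half-width (SD of change 1.2) | SE, change → adjusted (session SD 1.2) | Shift, dB |
|---|---|---|---|---|---|
| 0.3 | 0.65 | −0.59 | 0.72 | 0.518 → 0.418 | −0.42 |
| 0.5 | 0.75 | −0.50 | 0.78 | 0.438 → 0.379 | −0.30 |
| 0.7 | 0.85 | −0.39 | 0.83 | 0.339 → 0.313 | −0.18 |
| 0.9 | 0.95 | −0.22 | 0.87 | 0.196 → 0.191 | −0.06 |

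Simulation agreed: variance ratios 0.66, 0.77, 0.87 and 0.97. At rho 0.6 the imposed 0.6 dB imbalance shifted the change score by −0.244 (formula −0.24) and ANCOVA by −0.002.

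**4. Adding only a covariate-by-session term.** This recovers the ANCOVA estimate, but the Day 1 rows are now fitted exactly. With equal correlations across the four sessions and one pooled residual variance, the model takes the per-participant contrast variance as s²(1−rho)(3+rho)/2, against a true s²(1−rho)(1+rho). The ratio (3+rho)/(2(1+rho)) is 1.27, 1.17, 1.09 and 1.03 at the four correlations. Scaling 1.96 by its square root implies type I error of about 2.7%, 3.4%, 4.1% and 4.7%; simulation gave 2.7%, 3.4%, 4.0% and 4.7%.

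**The case against.** The strongest reply is that 9.4.2 does not say that the covariate enters as a main effect only. It borrows the covariate from an earlier trial whose model is not in these documents, and a session interaction may be intended. That stands as a condition on the conclusion. But a main effect is the natural reading, and the alternative has the fault in step 4, although that fault depends on a single residual variance, which the plan does not specify either.

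A reader might infer more than the documents support:

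- **That baseline is ignored.** It is not. Each participant's Day 1 value is subtracted, and a comparison of changes is what 9.1 hypothesises. Only the regression adjustment is missing.
- **That the primary test is invalid.** Under randomisation the change-score contrast is unbiased and holds its level; simulated type I error was 4.8% to 5.1%. Regression to the mean acts on all arms alike and reaches the contrast only through chance imbalance, so it is not a separate source of bias.
- **That the trial is underpowered because of this.** On the plan's own inputs, power is 0.995 even at 15 per arm, and a half-width of 0.90 is small beside a difference of 2.

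It is also fair that the gain rests on an unknown correlation and is slight at 0.9, and that this is a pilot with sensitivity analyses promised. Those analyses are generic, however, and 9.2 places the study's value largely in its point and interval estimates, which are what better adjustment would improve.

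**Conclusion.** The point holds for the model as written: Day 1 kept as a session level and baseline alpha power entered without a session interaction. The covariate then has no effect on the Day 1 to Day 5 arm contrast, and the adjustment for which the plan gives a reason is not made. With complete data the cancellation is exact; in the check with missing follow-up visits the estimate was unchanged and only its SE moved slightly.

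The cost is 5% to 35% of the contrast variance for correlations from 0.9 down to 0.3, plus a dependence on chance baseline imbalance. These sizes assume equal session variances and a correlation that the documents do not supply; the dB figures also depend on which SD the 1.2 represents. Validity and stated power are not in question. This should be fixed as a matter of specification and efficiency in the primary analysis; it does not undermine the trial.

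**What to change.** Amend 9.4.2 before unblinding, because choosing later between a change-score and a baseline-adjusted result would be data-driven. Either of two models serves:

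1. Take Day 1 out of the session factor. Model post-baseline alpha power in dB (Day 5, 2-week, 4-week) on arm, session, arm-by-session, baseline dB and baseline-by-session, with a participant random effect. Read the primary result from the baseline-adjusted Day 5 arm differences. The treatment-by-session interaction can no longer serve as the primary test, because among post-baseline sessions it asks only whether arm differences vary over time.
2. Keep Day 1 as a response, constrain the arm means to be equal at Day 1, and drop the covariate. The primary result is again the Day 5 arm contrast.

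In either case, state the covariance structure and name the pre-stimulation Day 1 recording as the baseline. Adding a covariate-by-session term while keeping Day 1 in the response is not a sufficient repair.

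The cost is analysis-plan wording only: no new data, visits or participants.
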